#### **10.4.2 Electrocardiograms**

Standard 12-lead ECGs (2 interpretable recordings [20 to 30 minutes apart]) will be performed throughout the study from Visit 1 (entry to study) to Visit 8, and at ETV in case of early termination. Standard 12-lead ECGs will also be performed at Visit 4 of the Transition Period, at week 18, 19, or 20 of the Taper Period, and at the Safety Follow-Up Visit.

Electrocardiograms will be reviewed locally and at a central ECG laboratory. If any abnormal finding is assessed by the investigator to be clinically significant, then the ECG should be repeated on the same day. If the clinically significant abnormality is confirmed by the repeat ECG, then the subject must be withdrawn from the study. The Investigator will determine whether the results of the ECG are normal or abnormal and assess the clinical significance of any abnormalities.

For ECGs, Baseline will be defined as the average of all pre-dose interpretable readings. For all post-Baseline visits, the average of all interpretable readings at the specified visit will be used for summaries.

Observed values of ECG results will be summarized for each visit and Last Visit. Change from Baseline in ECG results will be summarized for all post-Baseline visits, and Last Visit by treatment group, and will be repeated by treatment group and age group, and by treatment group and weight group using the levels defined in section 4.8.

The number and percentage of subjects with no abnormality, an abnormal but not clinically significant finding, and a clinically significant finding, will be summarized by treatment group at Visit 1 (entry to the study), Visit 2 (Baseline), and at each post-Baseline visit up to Visit 8, and Last Visit. Percentages will be relative to the number of subjects with an ECG assessment at each time point. Subjects are counted at most once at each time point based on the worst observed outcome across all abnormalities reported at that time point.

Summaries of shifts from Baseline to post-Baseline visits, and from Baseline to Last Visit, will also be provided by treatment group based on the categories normal, abnormal, not clinically significant, and abnormal, clinically significant.

A listing of ECG data will be provided for all subjects with other significant TEAEs in the Cardiac and ECG Related Terms category defined in Appendix 12 (section 12.2). A subject data listing of all ECG parameter values for all subjects will also be presented. Listings will include results from each recording and the average of all recordings.

The number and percentage of subjects with treatment-emergent ECG abnormalities will be presented by visit and treatment group. Abnormalities reported at an unscheduled visit will be summarized under the scheduled visit preceding the unscheduled visit (if the abnormality was not present already at the preceding scheduled visit). Treatment-emergent is defined as meeting the criteria at any post-Baseline visit during the Treatment Period (including unscheduled visits)

and not meeting the same criteria during Baseline. All ECG parameter values will be listed for subjects meeting any abnormality criteria.

Abnormality criteria to be used in the determination of ECG abnormalities are defined as follows, where increase and decrease are relative to Baseline values:

**Table 10–2: Electrocardiogram Abnormality Criteria**

Parameter	Age Range	Abnormality Criteria
QT interval (ms)	4y-<12y	≥500
	≥12y	≥500 or ≥60ms increase from Baseline
QTc(F) (ms)	4y-<12y	>440, or >15% increase from Baseline
	≥12y- <17y	>440, or >15% increase from Baseline
	≥17y	≥500 or ≥60ms increase from Baseline
QTc(B) (ms)	3y-<12y	>450, or >15% increase from Baseline
	≥12y- <17y	>450, or >15% increase from Baseline
	≥17y	≥500 or ≥60ms increase from Baseline
PR interval (ms)	3y-<12y	>180, or ≥25% increase from Baseline
	≥12y - <17y	>200, or ≥25% increase from Baseline
	≥17y	Treatment-emergent value >200, >220, >250
QRS interval (ms)	4y-<12y	>100, or ≥25% increase from Baseline
	≥12y - <17y	≥110, or ≥25% increase from Baseline
	≥17y	Treatment-emergent value >100, >120, >140
Heart rate (bpm)	3y-<12y	<60, >130
	≥12y	<50, >120

Abbreviations: bpm = beats per minute; m = months; ms = milliseconds; QTc = corrected QT interval; y = years. A month is defined as 30 days; a year is defined as 365.25 days.

A subject data listing will be provided that identifies subjects with a clinically significant finding after the first dose of study medication for each type of ECG abnormality.

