9. Subject is on a ketogenic or other specialized diet. If the subject was on a specialized diet in the past, they must be off the diet for ≥ 2 months prior to the Baseline Period.
10. Subject has an alanine aminotransferase (ALT), aspartate aminotransferase (AST), or total bilirubin level ≥ 2 times the upper limit of normal (ULN), or creatinine clearance less than 30mL/min.
11. Subject has a clinically relevant ECG abnormality, in the opinion of the investigator (eg, second or third degree heart block at rest or a corrected QT interval [QTc] greater than 450ms).

12. Subject has hemodynamically significant congenital heart disease.
13. Subject has an arrhythmic heart condition requiring medical therapy.
14. Subject has a known history of severe anaphylactic reaction or serious blood dyscrasias.
15. Subject has nonepileptic events that could be confused with seizures.
16. Subject has a current diagnosis of Lennox-Gastaut syndrome, primary generalized epilepsy, mixed seizure disorder (partial and primarily generalized seizures), or purely nocturnal seizures.
17. Subject has a history of convulsive status epilepticus ≤ 2 months prior to the Baseline Period.
18. Subject has been treated with vigabatrin and experienced any vision loss. Subjects who have received vigabatrin in the past must have documentation of an assessment for vision loss prior to study entry or documentation of why visual field testing cannot be performed.
19. Subject has been treated with felbamate and has experienced any serious toxicity issues (defined as liver failure, aplastic anemia) with this treatment. Subjects treated with felbamate for <12 months are excluded. Note: any subject who has been treated with felbamate for ≥ 12 months and has not experienced serious toxicity issues is eligible.
21. Subject has a medically documented history of alcohol or drug abuse.
22. Subject has a known cardiac sodium channelopathy, such as Brugada syndrome.
23. Subject has an acute or sub-acutely progressive central nervous system disease. Subject has epilepsy secondary to a progressing cerebral disease or any other progressively neurodegenerative disease (malignant brain tumor or Rasmussen Syndrome).

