6.3 Withdrawal criteria

Subjects are free to withdraw from the study at any time, without prejudice to their continued care.

Subjects **must** be withdrawn from this study if any of the following events occur:

1. Subject experiences intolerable AEs, including clinically relevant abnormal laboratory findings that, in the opinion of the investigator, preclude further participation in the study.
2. The sponsor or a regulatory agency requests withdrawal of the subject.
3. Subject has QTc interval ≥ 500 ms that is confirmed by a cardiologist overread on any ECG.
4. Subject develops a second degree atrioventricular (AV) block while awake or develops a third degree AV block.
5. For subjects ≥ 6 years of age, subject has actual suicidal ideation since last visit as indicated by a positive response ("Yes") to either Question 4 or Question 5 of the C-SSRS. The subject should be referred immediately to a Mental Healthcare Professional and must be withdrawn from the study.

6. Subject is unwilling or unable to continue, or the parent/legal representative is unwilling or unable to allow the subject to continue in the study.
7. Investigator decides that withdrawal from further participation would be in the subject's best interest.
8. Subject experiences convulsive status epilepticus.
9. Subject uses rescue medication in excess of that permitted by the protocol.
10. In the case of liver function test (LFT) results of transaminases (AST, ALT, or both) $\geq 3x$ ULN to $< 5x$ ULN and total bilirubin $\geq 2x$ ULN or transaminases (AST, ALT, or both) $\geq 5x$ ULN, the study medication must be immediately discontinued and the subject withdrawn from the study. The LFTs will be repeated as soon as possible, and in no case > 1 week later.
11. Female subject who achieves menarche and does not practice contraception as provided in Exclusion Criteria 6 unless sexually abstinent. Subject becomes pregnant, as evidenced by a positive pregnancy test.
12. Subject needs any alteration in AED daily dose or VNS settings.

Participation in this study may be discontinued for any of the following reasons:

1. Subject has any clinically relevant change in medical or psychiatric condition (if in the opinion of the investigator, the change in condition warrants discontinuation from the study).
2. Subject requires a medication that is not permitted by the protocol.
3. Subject and/or delegated caregiver is noncompliant with study procedures or medication, in the opinion of the investigator.

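### For subjects under 17, SAP Table 10-2 has no QTc 500 ms criterion, so a child with Baseline QTcF of 441 to 450 ms and QTcB above 450 ms can pass the protocol's 500 ms limit without being counted as treatment-emergent

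*SAP*

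**What the plan says.** **Entry.** Protocol 6.2, criterion 11, reads "Subject has a clinically relevant ECG abnormality, in the opinion of the investigator", and gives as one example "a corrected QT interval [QTc] greater than 450ms". No correction formula is named.

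**Withdrawal.** Protocol 6.3, criterion 3, requires withdrawal at a QTc of 500 ms or more "that is confirmed by a cardiologist overread on any ECG". Again no formula is named.

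**Tabulation.** SAP Table 10-2 sets these limits:

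- QTcF, both age bands under 17: ">440, or >15% increase from Baseline".
- QTcB, both age bands under 17: ">450, or >15% increase from Baseline".
- QTcF and QTcB at 17 years or older: "≥500 or ≥60ms increase from Baseline".
- Uncorrected QT: 500 ms or more at 4 to under 12 years. From 12 years, the same limit or a rise of 60 ms or more.

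**Treatment emergence.** SAP 10.4.2 requires the criteria to be met after Baseline during the Treatment Period "and not meeting the same criteria during Baseline". It does not say whether that means the whole table row or each limb of it. Baseline is the mean of all pre-dose readings, and each later value is the mean of the readings at that visit.

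**The concern.** The treatment-emergent ECG table is where QT risk is counted by arm. The trial enrols children under 17, so the 17-and-over QTc rows can apply only to someone who has a birthday during the study. The absolute limits that do apply lie at or below the entry example. A child who starts above them has already used up the absolute limb and can be counted only through a rise of more than 15%. From a Baseline near 450 ms, that rise ends above 500 ms.

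Two things are at stake. A few of the largest absolute QTc values may be missing from the by-arm count. For all other subjects under 17, a change from 439 to 441 ms and one from 400 to 505 ms satisfy the same QTcF criterion, so the table cannot show how many subjects in each arm reached 500 ms.

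**Working it through.** The documents give no figure to reproduce, so the check applies the Table 10-2 limits and the emergence rule to Baselines that the 450 ms example does not bar.

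**1. The QTcF row, limbs tested separately.** A Baseline of 441 to 450 ms already exceeds 440. The remaining limb begins above 1.15 × Baseline:

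- Baseline 441: 1.15 × 441 = 507.15 ms. Reaching 500 is a rise of 59/441 = 13.4%.
- Baseline 445: 1.15 × 445 = 511.75 ms. Reaching 500 is a rise of 55/445 = 12.4%.
- Baseline 450: 1.15 × 450 = 517.5 ms. Reaching 500 is a rise of 50/450 = 11.1%.

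The row therefore does not count values from 500 ms up to about 507 to 517.5 ms, depending on Baseline.

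**2. When the QTcB row is closed as well.** QTcF = QT/RR^(1/3) and QTcB = QT/RR^(1/2), with RR = 60/heart rate in seconds. Hence QTcB = QTcF × (heart rate/60)^(1/6). At QTcF 445, QTcB exceeds 450 when heart rate is above 60 × (450/445)^6 = 64.2 bpm. At QTcF 450 the figure is 60 bpm. At constant heart rate both corrections rise by the same percentage, so the 15% limb of the QTcB row does no better than that of the QTcF row.

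**3. Worked case.** QTcF goes from 445 to 505 ms at a constant 80 bpm (assumed), so RR = 0.75 and RR^(1/3) = 0.9086.

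| Row | Baseline | Later | Counted under 17? |
|---|---|---|---|
| QTcF | 445 | 505 (+13.5%) | No: above 440 at Baseline, rise not above 15% |
| QTcB | 466.9 | 529.8 (+13.5%) | No: above 450 at Baseline, rise not above 15% |
| QT | 404.3 | 458.8 (+54.5 ms) | No: below 500, and rise below 60 |

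The same rise is also uncounted at 66, 70, 90 and 100 bpm. It is counted at 60 and 64 bpm, where Baseline QTcB (445 and 449.8) is still within its limit.

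**4. Whole-row reading.** If the row is one criterion, a child above 440 at Baseline can never become treatment-emergent on QTcF. QTcF 445 to 530 at 80 bpm (+19.1%) would be counted with separate limbs but is not counted on either QTc row here. The uncorrected QT rows still set an eventual limit. Under 12 years at 80 bpm, QT reaches 500 only at QTcF 500/0.9086 = 550 ms. From 12 years, a QT rise of 60 ms corresponds to a QTcF rise of 60/0.9086 = 66 ms, so the child is counted from about 511 ms.

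**5. Averages against single recordings.** Two recordings of, say, 505 and 490 ms (illustrative) average 497.5 ms. The first reaches the 500 ms value in Protocol 6.3, which refers to any ECG; the visit value does not.

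**The case against.** The strongest reply is that the gap is narrow and the data are visible elsewhere. Much of this stands.

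- **It needs joint conditions.** Both QTcF above 440 and QTcB above 450 must hold at Baseline. If entry is judged on Bazett at 450 or below, the QTcB row stays open and counts the rise. The missing formula is what allows both conditions to hold together.
- **A fast heart rate alone does not hide the rise.** A reader might infer that any child with a high Baseline QTcB escapes the table. At 100 bpm and Baseline QTcF 420, QT is 420 × 0.6^(1/3) = 354 ms and QTcB is 457 ms, so the QTcB limit is already passed. The QTcF row is still open, however, and counts the child once QTcF passes 440, which is QTcB of about 440 × (100/60)^(1/6) = 479 ms.
- **Table 10-2 does contain 500 ms for under-17s, but only on uncorrected QT.** Those rows, and the 60 ms limb from 12 years, catch some cases. They do not catch the worked case.
- **The values are not lost from the report.** SAP 10.4.2 plans listings of every recording, visit summaries of values and changes (with maxima, under SAP 3.1), and counts by investigator assessment. A confirmed value also leads to withdrawal. None of these gives the number of subjects per arm at QTc 500 ms or more.
- **The 450 ms value is an example under investigator judgement.** This does not close the gap, because it leaves higher Baselines possible.
- **The SAP may set age-specific paediatric limits.** It may, and the existing rows need not be replaced.

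**Conclusion.** The point holds as a limited reporting gap. For subjects under 17, a child with Baseline QTcF of 441 to 450 ms and Baseline QTcB above 450 ms can pass the protocol's 500 ms value without being counted as treatment-emergent. With separate limbs the uncounted QTcF band ends at 507 to 517.5 ms. With the whole row as one criterion, the QTcF row has no upper end, and only the uncorrected QT rows eventually catch the child. The SAP does not say which reading applies.

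The worked figures assume a constant heart rate and entry not judged on Bazett at 450 ms. The number of children affected cannot be estimated, because the documents give no entry QTc distribution. A reader might infer that QT prolongation would be hidden from the report, or that the withdrawal rule is weakened. The documents support neither: the values are listed and summarised, and Protocol 6.3 operates independently of the table. What is missing is a count by arm at the protocol's own limit.

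**What to change.** Keep the existing rows of Table 10-2. For ages 4 to under 17, and for both QTcF and QTcB, add separate tabulation rows for 500 ms or more and for a rise of 60 ms or more from Baseline; the SAP already uses these limits from age 17. State in SAP 10.4.2 that each criterion is tested for treatment emergence on its own. Every rise from a Baseline of 450 ms or less to a visit average of 500 ms or more is then counted.

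Count 500 ms or more on any single recording as well as on the visit average, since Protocol 6.3 refers to any ECG, and state what counts as Baseline for that row. It would count recorded values, not overread-confirmed withdrawals, and should be labelled so.

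The cost is a few extra table rows from data already collected, best settled before unblinding.

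Separately, Protocol 6.2 criterion 11, Protocol 6.3 criterion 3 and Table 10-2 must be reconciled on which QTc each refers to. No correction formula or clinical threshold is proposed here. Any change to the entry or withdrawal wording could affect who enters or stays, so it is a matter for the protocol and not for the SAP.

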### 10.4.3 Physical examination

#### 10.4.3.1 Complete physical examination

A complete physical examination will be performed at Visit 1 (entry to study), Visit 2 (Baseline), Visit 8, and at ETV in case of early termination. A complete physical examination will also be performed at Visit 4 of the Transition Period and at the Safety Follow-Up Visit.

The complete physical examination will include cardiac and respiratory function via auscultation; temperature measurement, and review of all body systems.

Clinically significant physical examination findings will be reported as AEs.

### **10.4.3.2 Brief physical examination**

A brief physical examination will be performed at Visit 3 to Visit 7. A brief physical examination will also be performed at Visit 1 to Visit 3 of the Transition Period, and at Week 18, 19, or 20 of the Taper Period, as appropriate.

The brief physical examination will include a review of the following body systems:

- Cardiovascular
- Pulmonary
- Abdominal (hepato-gastrointestinal)
- Dermatologic

Clinically significant physical examination findings will be reported as AEs.

### **10.4.4 Neurological examination**

#### **10.4.4.1 Complete neurological examination**

A complete neurological examination will be performed at Visit 1 (entry to study), Visit 2 (Baseline), Visit 8, and at ETV in case of early termination. A complete neurological examination will also be performed at Visit 4 of the Transition Period and at the Safety Follow-Up Visit.

The complete neurological examination will include selected assessment of: general neurological status (level of consciousness, mental status, speech), cranial nerves, reflexes, motor system (general motor status, muscle strength, muscle tone), coordination/cerebellar function, and sensation.

Summaries of shift from Baseline to Last Visit will be provided by treatment group based on categories normal, abnormal, not clinically significant, and abnormal, clinically significant. A listing of abnormal neurological examination findings from the complete neurological examination will also be provided.

Clinically significant neurological findings will be reported as AEs.

#### **10.4.4.2 Brief neurological examination**

A brief neurological examination will be performed at Visit 3 to Visit 7. A brief neurological examination will also be performed at Visit 1 to Visit 3 of the Transition Period, and at Week 18, 19, or 20 of the Taper Period, as appropriate.

The brief neurological examination will include selected assessment of: general neurological status, reflexes, muscle strength, and coordination/cerebella function.

A listing of abnormal neurological examination findings from the brief neurological examination will also be provided. No summaries of the brief neurological examination findings are planned.

Clinically significant neurological findings will be reported as AEs.

### **10.4.5 Vagus nerve stimulation**

Vagus nerve stimulation status is recorded throughout the study from Visit 1 (entry to study) to Visit 8, and at ETV in case of early termination, and at unscheduled visit, only for subjects with

an implanted VNS device. VNS status will also be assessed during the Transition Period, Taper Period, and at the Safety Follow-Up Visit only for those patients with an implanted VNS device.

A listing of VNS status will be provided only for those subjects with an implanted VNS device. No summaries of VNS data are planned.

#### 10.4.6 Tanner stage assessment

The investigator will evaluate the subject's sexual development using the 3-item Tanner scale (ie, for females: breasts, pubic hair, and overall stage; and for males: genitals, pubic hair, and overall stage). The investigator should use clinical judgment in deciding which subjects are selected for evaluation of Tanner stage (ie, those subjects who are pubescent at Visit 1 [entry to study] or who will enter puberty during the course of the study).

Tanner stage will be assessed at Visit 1 (entry to study) and at Visit 8, and at ETV in case of early termination.

A shift table will be produced showing the change in overall Tanner stage (1-5) from Baseline to Last Visit, by sex and treatment group.

#### 10.4.7 Achenbach Child Behavior Checklist

The Achenbach Child Behavior Checklist (CBCL) is completed at Visit 2 (Baseline), Visit 5 (End of Titration Period), Visit 8, and at ETV in case of early termination.

The Achenbach CBCL form is a questionnaire intended to evaluate a child's competencies and behavioral/emotional problems. Depending on the subject's age, 1 of 2 versions of the Achenbach CBCL is used. The CBCL/1½-5 is intended for use in children 18 months to 5 years and 11 months of age. For subjects ≥6 years to <17 years, the CBCL/6-18 will be used. For each subject, the same version (CBCL/1½-5 or CBCL/6-18) that is used at Visit 2 (Baseline) should be used at Visit 5, and Visit 8/ETV, and should be completed by the same parent/legal representative.

The CBCL/1½-5 comprises 100 questions and the CBCL/6-18 comprises 120 questions with the response options of:

- 0=not true (as far as known)
- 1=somewhat of sometimes true
- 2=very true or often true

The CBCL/1½-5 will be grouped according to syndrome scales in [Table 10-3](#) and the CBCL/6-18 will be grouped according to empirically based syndrome scales in [Table 10-4](#).

**Table 10-3: CBCL/1½-5**

Syndrome scale	Questions
Aggressive behavior	8, 15, 16, 18, 20, 27, 29, 35, 40, 42, 44, 53, 58, 66, 69, 81, 85, 88, 96
Anxious/depressed	10, 33, 37, 43, 47, 68, 87, 90
Attention problems	5, 6, 56, 59, 95

**Table 10–3: CBCL/1½-5**

Syndrome scale	Questions
Emotionally reactive	21, 46, 51, 79, 82, 83, 92, 97, 99
Sleep problems	22, 38, 48, 64, 74, 84, 94
Somatic complaints	1, 7, 12, 19, 24, 39, 45, 52, 78, 86, 93
Withdrawn	2, 4, 23, 62, 67, 70, 71, 98
Other problems	3, 9, 11, 13, 14, 17, 25, 26, 28, 30, 31, 32, 34, 36, 41, 49, 50, 54, 55, 57, 60, 61, 63, 65, 72, 73, 75, 76, 77, 80, 89, 91, 100

**Table 10–4: CBCL/6-18**

Syndrome scale	Questions
Aggressive behavior	3, 16, 19, 20, 21, 22, 23, 37, 57, 68, 86, 87, 88, 89, 94, 95, 97, 104
Anxious/depressed	14, 29, 30, 31, 32, 33, 35, 45, 50, 52, 71, 91, 112
Attention problems	1, 4, 8, 10, 13, 17, 41, 61, 78, 80
Rule-breaking behavior	2, 26, 28, 39, 43, 63, 67, 72, 73, 81, 82, 90, 96, 99, 101, 105, 106
Social problems	11, 12, 25, 27, 34, 36, 38, 48, 62, 64, 79
Somatic complaints	47, 49, 51, 54, 56a, 56b, 56c, 56d, 56e, 56f, 56g
Thought problems	9, 18, 40, 46, 58, 59, 60, 66, 70, 76, 83, 84, 85, 92, 100
Withdrawn/depressed	5, 42, 65, 69, 75, 102, 103, 111

Standardized T-scores are determined for each subject’s raw syndrome and overall scores based on the subject’s age and sex. Tables mapping each raw score to the appropriate T-score are provided in the CBCL Professional Manual and will be reproduced programmatically.

Calculated T-score values and change from Baseline for each CBCL/1½-5 syndrome (aggressive behavior, anxious/depressed, attention problems, emotionally reactive, other problems, sleep problems, somatic complaints, and withdrawn) will be summarized for each visit, and Last Visit, by treatment group.

Calculated T-score values and change from Baseline for each CBCL/6-18 syndrome (aggressive behavior, anxious/depressed, attention problems, rule-breaking behavior, social problems, somatic complaints, thought problems, and withdrawn/depressed) will be summarized for each visit, and Last Visit, by treatment group.

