11.9.7 Achenbach CBCL

The Achenbach CBCL is a widely used validated questionnaire to evaluate a child's competencies and behavioral/emotional problems. Behavioral problems will be scored by the

parent(s)/legal representative(s). Depending on the subject's age, 2 versions of the CBCL will be used. The CBCL/1½-5 checklist is intended for use in children 18 months to 5 years and 11 months of age. For subjects ≥ 6 years to < 17 years of age at Screening, the CBCL/6-18 version will be used. The Achenbach CBCL will only be administered in countries where a translated version is available.

For each subject, the same version of the scale that is completed at Visit 2 (Baseline) should be maintained for the duration of the study in accordance with the tabular schedules of study procedures (Section 5.2) and should be completed by the same parent/legal representative. The completion of the Achenbach CBCL will require approximately 45 minutes.

In both questionnaires, the occurrence of certain problems and behaviors in the past 6 months will be scored on the following scale:

- 0=not true (as far as known)
- 1=somewhat or sometimes true
- 2=very true or often true

Eight syndrome scores will be calculated from these questions, which will in turn be summarized by 2 composite scores. Additionally, for each score on the question, syndrome, and total level, categorizations based on a normative sample will be used to evaluate normal, borderline, or clinically relevant behavior.

In addition, the Achenbach CBCL/6-18 includes ratings related to performance in school, activities in leisure time, and special interests.

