### **3.9 Changes to protocol-defined analyses**

There are no changes to analyses specified in the protocol.

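### SAP 10.4.7 tabulates only CBCL syndrome T-scores; the composite, total and normative-category outputs of Protocol 11.9.7 are left out, and SAP 3.9 does not declare it

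*SAP*

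**What the plan says.** Protocol 11.9.7 sets out how the CBCL is scored and used. "Eight syndrome scores will be calculated from these questions, which will in turn be summarized by 2 composite scores". It goes on that "for each score on the question, syndrome, and total level, categorizations based on a normative sample will be used" in order "to evaluate normal, borderline, or clinically relevant behavior".

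Protocol 13.4.1 lists the CBCL among the variables that assess safety. It asks for numbers and percentages by treatment group when safety data are categorical, and it makes shift tables optional.

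SAP 10.4.7 groups the items into syndrome scales (Tables 10-3 and 10-4) and derives T-scores from each child's "raw syndrome and overall scores based on the subject" (the sentence continues with age and sex). It then has two summary sentences, one per CBCL version. The one for older children covers "Calculated T-score values and change from Baseline for each CBCL/6-18 syndrome"; the other does the same for the CBCL/1½-5 scales. Neither goes beyond the individual scales.

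SAP 3.1 defines a continuous summary as n, mean, SD, median, minimum and maximum, and promises listings of all documented and calculated data. SAP 3.9 says: "There are no changes to analyses specified in the protocol".

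**The concern.** The protocol names three CBCL outputs that the SAP does not tabulate: the composites, the total score, and the normative categories. SAP 3.9 says nothing about this, and neither SAP amendment log records a decision to leave them out, although Amendment 2 corrected an item number in this same section.

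The CBCL is the only behavioural assessment among the safety variables in Protocol 4.2.2. A reader of the study report will want to know how many children on lacosamide, compared with placebo, are in the clinically relevant range and how many moved there on treatment. No planned table answers that. If the cut-offs are chosen only when somebody asks, they will be chosen after the data are known.

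**Working it through.** The documents state no CBCL figure, so there is nothing to reproduce. The check is a comparison of texts.

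| Output | Protocol | SAP 10.4.7 |
|---|---|---|
| Syndrome scores | To be calculated (11.9.7) | T-score and change summarized by visit, Last Visit and arm |
| 2 composites | To summarize the syndromes (11.9.7) | Not defined in Tables 10-3 or 10-4; not summarized |
| Total score | Named as a level to be categorized (11.9.7) | Overall T-score derived; absent from both summary sentences |
| Normal, borderline, clinically relevant | To be used at question, syndrome and total level (11.9.7) | Not derived or tabulated |
| Counts per category by arm | Rule for categorical safety data (13.4.1) | None for the CBCL |
| Shift table | Optional (13.4.1) | None for the CBCL |

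The SAP treats the neighbouring BRIEF-P and BRIEF differently: Section 10.4.9 summarizes the index scores and the Global Executive Composite. For the CBCL it summarizes the lowest level and stops there.

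**Can the planned statistics stand in for counts?** The following is an illustration on assumed inputs, except for the arm size. About 300 randomized 1:1 (Protocol 5.1.2 and 5.1) gives 300 / 2 = 150 per arm, and all are taken to have CBCL data. Assume a fraction f of the lacosamide arm worsens by s = 10 T-score points and nobody else shifts on average, with an SD of change of 5 to 10.

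- Mean shift = f × s.
- SD in the lacosamide arm = √(SD² + f(1−f)s²).
- SE of the difference = √(SD²/n + (SD² + f(1−f)s²)/n).

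At f = 10%, f(1−f)s² = 0.10 × 0.90 × 100 = 9 and the mean shift is 1.0 point. With SD 5, SE = √((25 + 34)/150) = 0.63. With SD 10, SE = √((100 + 109)/150) = 1.18.

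| f | Children affected | Mean shift | SE (SD 5 to SD 10) | Shift / SE (SD 10 to SD 5) |
|---|---|---|---|---|
| 5% | 7 to 8 | 0.5 | 0.60 to 1.17 | 0.4 to 0.8 |
| 10% | 15 | 1.0 | 0.63 to 1.18 | 0.85 to 1.6 |
| 15% | 22 to 23 | 1.5 | 0.65 to 1.19 | 1.3 to 2.3 |

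The SD gives little away: at 10% it rises from 5 to 5.8, or from 10 to 10.4. The maximum shows the single worst child, not how many worsened. The actual n will be smaller, because the two versions are summarized separately and the scale is used only where a translation exists.

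The children affected are those who worsen. How many would change category depends on where they started and on the cut-offs, and the documents give neither.

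**Recall period.** The CBCL asks about the past 6 months, about 26 weeks. At Visit 5 (Week 6), about 26 − 6 = 20 of those weeks precede dosing (77%). At Visit 8 (Week 16), about 26 − 16 = 10 do (38%). On-treatment change is diluted in every CBCL output, categories included.

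**The case against.** The best defence is that 11.9.7 describes an instrument, while planned analyses belong to Section 13. There the CBCL appears only in a list of other safety variables, and detail is deferred to the SAP. It is not a primary safety variable: adverse events are, and SAP 10.2 tabulates them by system organ class and preferred term. BRIEF, the closest parent-rated T-score instrument, has no category table either.

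Part of this stands. Because shift tables are optional in 13.4.1, the lack of one is not in itself a departure. Four stronger readings that a reader might reach also fail:

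- **That only means are reported.** SAP 3.1 adds SD, median, minimum and maximum.
- **That worsening in a minority would be invisible.** The listings carry each child's calculated values and change from Baseline, and clinically evident worsening can be reported as an adverse event.
- **That the total score is dropped altogether.** An overall T-score is derived and so falls under the listings; it is simply not tabulated.
- **That a particular number of children would be missed.** Any such number is an assumption.

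The rest of the defence does not hold. Section 11.9.7 states its outputs as things that will be done, and 13.4.1 then says how categorical safety data are presented. Deferring detail to the SAP does not cover leaving a stated output out while declaring no changes. The BRIEF comparison does not help, since Protocol 11.9.9 asks for no normative categories. Nor do the listings fill the gap: composites and categories that are never derived will not be in them, so a reader would have to classify children by hand.

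**Conclusion.** The point holds as a gap in descriptive safety reporting. SAP 10.4.7 leaves out the 2 composites, any summary of the overall score, and the normative categories, and SAP 3.9 does not acknowledge it. The result is that no table gives, by arm, the number of children in or entering the borderline or clinically relevant range. The text comparison alone carries this conclusion.

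The arithmetic shows only that, on assumed inputs, worsening in about 5% to 10% of an arm can shift the mean by less than about 1.6 standard errors. It does not show that such an effect exists or how large it is. The documents do not say that behavioural effects concentrate in a subset of children. The primary efficacy analysis is unaffected.

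**What to change.** In SAP 10.4.7, for each CBCL version:

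- Define the 2 composites, and summarize T-score and change for both composites and the total score as is already planned for the syndromes.
- Tabulate the number and percentage of children in each normative category by treatment group at Baseline, Visit 5, Visit 8 and Last Visit, for syndrome and total scores. A Baseline-to-Last-Visit shift table is the preferable layout, though the protocol does not require one.
- Write the category cut-offs and their source into the SAP before unblinding. The SAP cites the manual only for the raw-to-T conversion tables, and the documents do not show the cut-offs.
- Note the 6-month recall period beside the Visit 5 and Visit 8 results.

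In SAP 3.9, declare and justify any output described in 11.9.7 that will not be produced. Question-level categories are the likely candidate.

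The cost is a few extra descriptive tables. The data are already collected at these visits, the T-score tables are already to be programmed, and neither the protocol nor the visit schedule changes.
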